6.1 Name and description of IMP(s)

Specific details regarding the IMP(s) used in each country is elaborated in the appendices. New dosage-based arm(s) or drugs might be added or removed following review and approval by relevant regulatory authorities. Each label for an IMP (active drug or placebo) will include the description of the study product and the information of the source (manufacturer/supplier, batch/lot number and expiry or best use by date).

Placebo will be aligned to the active IMP in terms of dosing schedule. The interventions will be continued for (up to) 60 days from enrolment; or until the participant is diagnosed with COVID-19; or development of a complication or safety concern or side effect necessitating stopping the intervention; or the intervention arm is stopped; or participants are no longer at risk of contact with SARS-CoV-2 infected patients (e.g. no longer new COVID-19 cases at the participating site). Treatment groups may be discontinued at interim analyses, and new treatment groups might be initiated. If a treatment group is discontinued due to perceived harm, participants in that group will be informed as soon as possible to stop taking the IMP.

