11.2 Sample size and recruitment

11.2.1 Sample size calculation

We considered different event rates, depending on the following assumptions. Firstly, we assumed that 30-50% of the participants may become infected with SARS-CoV-2 over the course of the study period. Of these, the percentage of participants who will experience the primary endpoint or laboratory test-confirmed symptomatic COVID-19 (i.e. any of the following: cough, shortness of breath or difficulty breathing, fever, chills, muscle pain, sore throat, new loss of taste or smell, nausea, vomiting, or diarrhea) is uncertain. We use a range of 15-50%. The estimated event rate is therefore $0.15 * 0.30 = 0.045$ (or 4.5%, rounded to 5%) to $0.50 * 0.50 = 0.25$.

We declare the superiority of a treatment arm if the probability that the Odds Ratio (OR) of the treatment is less or equal to 1 is greater than 95%, i.e. $P(OR < 1) > 95\%$. The remaining Bayesian statistical triggers of the adaptive trial are specified in section 11.5.

A 2-arm trial was simulated to assess the required sample size for the study. The OR was assumed to be 0.7. Three event rates for control arm were used: 5%, 10% and 15%. We are interested in the lower end of the 5-25% range for the control rate since a higher sample size is required when the event rate in the control arm decreases for a given effect size.

Figure 5 below reports the probability that the simulated trial concludes superiority of the treatment arm depending on the sample size per arm.

[figure not shown]

Figure 5: Sample size estimation for the first phase of the trial (2-arm)

The simulations show that the probability of declaring efficacy depends on the event rate in the placebo arm. With 2000-2500 participants per arm, even if the event rate is 5% in the control arm, the study has >80% chance to declare efficacy.

We propose to retain the option of reaching a maximum of 2,500 participants per arm. We will aim to enrol a maximum of 5,000 participants in total in the first phase of the trial to allow for possible loss-to-follow-up (LTFU), withdrawal, protocol deviation, non-adherence and other methodological challenges. Further phases may be added to the trial until a maximum of 30,000 participants is reached.

The assumptions underlying the sample size calculations will be reviewed at each interim analysis based on the observed data.

11.2.2 *Planned recruitment rate*

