11.5 Interim analyses

This Bayesian trial will perform frequent interim analyses for efficacy, futility and harm. This means that the DMC will regularly consider the balance of benefit and risk. Strong evidence of benefit, futility, or harm will result in the advice to modify or stop the trial.

The objective of interim analyses is two-fold: 1/ identify whether an active arm is futile, if the probability that its $OR \geq 0.9$ is high, greater than 95%, 2/ identify whether there is sufficient evidence that an active arm is superior to the control arm. The following table contains the statistical triggers for efficacy, futility and harm at interim analyses and for the final analysis.

Probability	Threshold at interim analysis	Threshold at final analysis	Evidence for:
$P_1 = P(OR < 0.8 \mid \text{data})$	99%	95%	Marked clinical benefit
$P_2 = P(OR \geq 0.9 \mid \text{data})$	99%	95%	Non clinically relevant (i.e. futile) treatment (or harm when $OR \geq 1$)

Posterior predictive probabilities will also be calculated at each interim analysis to inform the potential adaptation decisions.

Platform trial

In the study there exists a possibility of adding treatment arm(s) at interim analysis or during the course of the study. If a treatment arm is added, all comparisons will be made with concurrent control participants.

For the main effects of individual treatments (i.e. when given on their own), the thresholds for superiority and futility described above will apply to the same manner to the additional treatment(s).

For treatments that are given in combination in the context of a potential factorial design, the quantity of interest will be $P(\text{interaction term} < 1 \mid \text{data}) \geq 0.95\%$ (or 99% at interim analysis) to declare evidence of synergy. The prior distribution for the interaction term will be specified in exactly the same way as the prior of the OR of the individual treatments. Only its interpretation changes.

The SAP contains additional details regarding the monitoring of the trial, including the cumulative probability of declaring efficacy depending on the underlying simulated hazard ratio.

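### Section 11.5 gives harm no trigger of its own: under one reading of the side note on the futility row, a no-effect agent is labelled harmful in about 20–38% of final analyses, under the other in about 5%

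*Combined protocol and SAP*

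**What the plan says.** Section 11.5 introduces its trigger table with the sentence "The following table contains the statistical triggers for efficacy, futility and harm at interim analyses and for the final analysis". The table has two rows:

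- P1 = P(OR < 0.8 | data), evidence of marked clinical benefit.
- P2 = P(OR ≥ 0.9 | data), whose evidence cell reads "Non clinically relevant (i.e. futile) treatment (or harm when" OR ≥ 1).

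Both rows use 99% at interim and 95% at the final analysis. No row gives P(OR ≥ 1 | data) or P(OR > 1 | data). The same section calls the purpose of the interim analyses two-fold and lists only futility and superiority. For added arms it carries forward only the superiority and futility thresholds. The Summary (section 2) nevertheless says that stopping rules for efficacy, harm and futility are specified.

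Section 6.1 attaches a step to a harm stop: "If a treatment group is discontinued due to perceived harm, participants in that group will be informed as soon as possible" to stop taking the product. It states no matching step for futility.

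**The concern.** P2 measures how sure one is that a relevant benefit is absent. It does not measure how sure one is that risk is increased. Attaching the harm label to that row leaves two possible rules:

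- **Reading A:** P2 crosses its threshold and the estimated OR is at least 1.
- **Reading B:** the margin moves from 0.9 to 1, so that P(OR ≥ 1 | data) must itself reach 99% or 95%.

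The text does not choose between them, and they behave very differently for an agent that does nothing. Ineffective and harmful are different conclusions to publish about widely used agents, and the DMC must be able to tell them apart.

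**Working it through.** **Inputs from the plan.** Section 11.2.1: at most 2,500 per arm; control rates of 5%, 10% and 15% simulated, within a considered range of 5–25%; OR 0.7 for power. Section 11.3: 1:1 allocation. Section 11.4.2: prior on the treatment OR centred on 1. Section 11.5: thresholds of 99% and 95%.

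**Assumptions.** A near-flat prior, because its spread is not given in the documents; a normal approximation to the posterior of the log OR; no covariates or site effects; true OR = 1. Section 11.5 speaks of "frequent interim analyses for efficacy, futility and harm" without giving their number or timing, so these are varied below.

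**Step 1: the plan's own figure.** The superiority rule asks that the probability of an OR "less or equal to 1 is greater than 95"%, which under a near-flat prior is about a one-sided 5% test. OR 0.7 on a 5% control rate gives odds 0.05/0.95 × 0.7 = 0.0368, a rate of 3.55%. With 2,500 per arm the SE of the difference is √[(0.0475 + 0.0343)/2500] = 0.00572. Then z = 0.01447/0.00572 − 1.645 = 0.885, and power is 81.2%. At 2,000 per arm it is 73.1%. The stated figure of more than 80% reproduces at the upper end of the plan's 2,000–2,500 range, so the approximation is adequate here.

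**Step 2: Reading A at the final analysis, true OR = 1.**

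- SE = √[2/(n p (1 − p))]
- P2 reaches 95% when the observed OR is at least 0.9 × exp(1.645 × SE)
- Probability of firing = 1 − Φ(ln 0.9/SE + 1.645), with ln 0.9 = −0.1054
- At that boundary, P(OR ≥ 1 | data) = Φ(ln 0.9/SE + 1.645)

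For a 5% control rate: SE = √(2/118.75) = 0.1298; −0.1054/0.1298 + 1.645 = 0.833; 1 − Φ(0.833) = 20.2%.

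| Control rate | SE | Observed OR needed | P2 ≥ 95% fires | P(OR ≥ 1) at boundary |
|---|---|---|---|---|
| 5% | 0.1298 | 1.114 | 20.2% | 0.80 |
| 10% | 0.0943 | 1.051 | 29.9% | 0.70 |
| 15% | 0.0792 | 1.025 | 37.6% | 0.62 |
| 25% | 0.0653 | 1.002 | 48.7% | 0.51 |

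The OR needed is above 1 in every row, so requiring an estimate of at least 1 removes nothing. Every futility call would also be a harm call, with as little as 0.51 to 0.80 posterior probability that the OR is at least 1.

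**Step 3: Reading A at one 99% interim look with 1,250 per arm.** The same formula with 2.326 in place of 1.645. For 5%: SE = √(2/59.375) = 0.1835; −0.574 + 2.326 = 1.752; about 4%. The figures are about 6% at a 10% control rate and 8% at 15%.

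**Step 4: Reading B.** The rate is 1 − Φ(1.645) = 5.0% at a single final analysis and 1 − Φ(2.326) = 1.0% at a single interim look, whatever the control rate.

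**Step 5: sensitivity.**

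- *Number of analyses.* With 3 to 10 equally spaced analyses (99% interim, 95% final), simulation gives, under Reading A, 22–24% at a 5% control rate, 31–33% at 10% and 39–41% at 15%. Under Reading B it gives about 5.5–7%.
- *Interim looks alone.* With 2 to 10 analyses in total, Reading A gives 4–13%, 6–19% and 8–24% at the same control rates; Reading B gives about 1–4%.
- *Prior.* A prior SD of the log OR from 10 down to 0.2 moves the single-final-analysis Reading A figures only to 20–21% (5% control rate) and 38–41% (15%).

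**The case against.** The strongest reply is that OR in the table is always the unknown parameter inside a posterior probability. No trigger is defined on a point estimate, so the note may be shorthand for P(OR ≥ 1 | data). That stands as a possible reading, and it is why the larger rates are conditional. It does not settle the matter, because P2 is the only probability printed in the row and the only one given thresholds.

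A reader might infer that the plan as written has a false-harm rate of 20–38% where its thresholds promise 5%. The documents do not support that. The figure needs Reading A and belongs to the final analysis; an early stop would run on the 99% trigger. A 95% threshold on P2 corresponds to about 5% crossings at a true OR of 0.9, not 1.0. At OR = 1 the agent lacks a relevant benefit, so P2 firing is right as a futility call.

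A reader might also infer serious consequences from section 6.1. Those are modest. That section refers to perceived harm without citing P2, and it ends the intervention when an arm is stopped for any reason. The first-phase agent is a vaccine given as a single dose (sections 3 and 6.4).

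The triggers lead only to advice, and the DMC also reviews safety (sections 8.9, 8.11 and 13.2). That limits the damage, but section 8.11 refers to a safety trigger without defining one, and none of these sections defines harm on the primary endpoint. The more detailed SAP announced in section 11.4 is not among the documents and might resolve the wording. Even so, section 11.5 says that this table contains the triggers.

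**Conclusion.** The point holds in conditional form. Harm is promised as a pre-specified trigger but has no probability or threshold of its own, however the note is read. Under Reading A, a no-effect agent would carry the harm label at a single final analysis in about 20% (5% control rate), 30% (10%) or 38% (15%) of trials, rising to 49% at the top of the plan's range. At one mid-trial interim look it is about 4–8% for control rates of 5–15%. Under Reading B the rates are about 5% and 1%.

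These figures rest on 2,500 per arm at the final analysis, 1,250 at the assumed interim and a near-flat prior. What is at stake is the label and the conclusion drawn, not whether an ineffective arm should be dropped. The change is worth making because one natural reading cannot separate ineffective from harmful and the repair is nearly free.

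**What to change.** 1. Delete the side note on harm from the P2 row.
2. Add a row P3 = P(OR > 1 | data) with its own interim and final thresholds, for example the table's existing 99% and 95%.
3. State that an arm is described as harmful on the primary endpoint only when P3 is met, and as futile when only P2 is met. Apply the same rule to added arms.
4. State that P3 does not replace the DMC's separate safety review.
5. While editing, reconcile the futility threshold. The text before the table, describing the interim objective, says the P2 probability "is high, greater than 95%, 2/ identify whether there is sufficient evidence", whereas the table gives 99% at interim.

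No stopping protection is lost. P(OR ≥ 0.9 | data) is never smaller than P(OR > 1 | data), so at equal thresholds any arm that meets P3 also meets P2. The cost is one table row and a sentence or two, computed from the same posterior with no extra data.

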The coronavirus disease 2019 (COVID-19) pandemic is a major public health crisis. As a bridge to specific vaccine development and rollout, we urgently need to deploy practical, affordable and effective interventions that prevent infection and / or mitigate the severity of COVID-19. The **CROWN** (COVID-19 Research Outcomes Worldwide Network) **COLLABORATIVE** is an international, transdisciplinary, research network, established to assess rigorously and efficiently promising interventions for COVID-19. **CROWN CORONATION** (COVID-19 Research Outcomes Worldwide Network for **CORONA**virus prevention**TION**) is a Bayesian, pragmatic, participant-level randomized, multi-center, and international placebo-controlled platform trial, assessing candidate interventions that either modify the host immune response or target the virus implicated in COVID-19 - severe acute respiratory syndrome coronavirus-2 (SARS-CoV-2). The objective of CROWN CORONATION is the prevention of symptomatic COVID-19 by using combinations of approved and safe agents, with complementary mechanisms of action. The primary outcome of CROWN CORONATION is symptomatic COVID-19 by day 60 after commencement of study intervention (i.e. any of the following: cough, shortness of breath or difficulty breathing, fever, chills, muscle pain, sore throat, new loss of taste or smell, nausea, vomiting, or diarrhea) with laboratory confirmation (i.e. based on viral polymerase chain reaction). The study design is scientifically compelling and ethically robust. Study arms that are 'under-performing' may be discontinued, and additional prophylactic arms may be added. This efficient approach can limit participant allocation to futile or even harmful study arms. The CROWN COLLABORATIVE has partners across the translational continuum, spanning foundational basic science discovery, proof-of-principle human research, pragmatic effectiveness trials, and public health focused implementation science.

Contents

Abstract	5
Contents.....	6
List of abbreviations.....	8
1 Trial personnel.....	10
2 Summary	13
3 Background and Rationale.....	15
3.1 Assessment and management of risk.....	19
4 Objectives	20
5 Trial design.....	20
5.1 Overall design.....	20
6 Investigational Medicinal Products (IMPs) and Non-Investigational Medicinal Products.....	24
6.1 Name and description of IMP(s).....	24
6.2 Source of IMP(s), Manufacture, Distribution and Storage	25
6.3 Storage and handling of IMP(s) at site.....	25

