11.4.2 Primary outcome analysis

The threshold for declaring that an education and surveillance plus therapeutic agent(s) arm is superior to education and surveillance plus placebo will be based on the OR for the specific arm compared to education and surveillance plus placebo. The objective is to obtain sufficient certainty (95% at least) that $OR < 1$. In mathematical terms, this quantity is referred to as $P(OR < 1) > 95\%$.

Primary analysis models:

The primary endpoint of incidence of symptomatic laboratory-confirmed COVID-19 infection will be analysed using a Bayesian logistic regression, including as covariates the treatment arm, age (<50 vs. ≥50), and a random effect for site.

The prior distribution corresponding to the education and surveillance plus placebo arm will be such that it is centered on 15% for the event rate, midway between the 5%-25% range that we consider. The prior distribution corresponding to the OR of the treatment arm will be such that the OR is centered on 1. Further details on the prior distributions are provided in the SAP.

Additional multivariable analyses will be conducted, taking into account the following variables: sex, smoking, body mass index, HIV infection, pre-existing respiratory disease, diabetes (recent HbA1c), hypertension, and coronary artery disease.

Secondary outcomes:

The endpoint of severity of symptoms on the WHO scale will be analysed using a Bayesian proportional odds model, using the same adjustment approach as the primary endpoint.

Other secondary outcomes that are binary in nature will be analysed using Bayesian logistic regression, using the same adjustment methods as previously described.

In addition, time-to-event models will be used to assess the effect of the interventions on the time to incidence of symptomatic laboratory-confirmed COVID-19 infection over the 150-day period since receiving trial interventions.

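### Sections 11.4.2 and 11.5 conflict on combination arms: read as written, the platform text of 11.5 leaves them with an interaction criterion that does not measure benefit against placebo and with no numerical futility or harm trigger

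*Combined protocol and SAP*

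**What the plan says.** **Arms.** Section 3, part D, plans a 2-arm start, then a 2-by-2 design, then a 2-by-2-by-2 design. Arm 4 is a combination in the second phase. Arms 4, 6, 7 and 8 are combinations in the third, so 4 of 8. The abstract puts combinations at the centre: "The objective of CROWN CORONATION is the prevention of symptomatic COVID-19 by using combinations of approved and safe agents".

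**General rule.** Section 11.4.2 sets "The threshold for declaring that an education and surveillance plus therapeutic agent(s) arm is superior". The decision there rests "on the OR for the specific arm compared to education and surveillance plus placebo". The criterion is P(OR<1) above 95%. The optional plural for agents takes in combination arms.

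**Interim rule, opening of 11.5.** One aim is to "identify whether there is sufficient evidence that an active arm is superior to the control arm". The other is to find futile active arms. The table sets P(OR<0.8) and P(OR≥0.9) against 99% at interim and 95% at the final analysis. Nothing there excludes combinations.

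**Platform text, later in 11.5.** The paragraph on single agents reads: "For the main effects of individual treatments (i.e. when given on their own), the thresholds for superiority and futility described above will apply". It extends them to treatments added later. The next paragraph reads: "For treatments that are given in combination in the context of a potential factorial design, the quantity of interest will be". What it then names is the posterior probability of an interaction below 1, with a final threshold printed as 0.95% (read here as 95%) "or 99% at interim analysis) to declare evidence of synergy". This paragraph gives no OR against placebo for a combination and no futility or harm threshold.

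**The concern.** Two parts of the plan speak to the same arms and name different quantities. The more specific text, the platform paragraph, names the one that does not answer the trial's question. For two agents A and B the interaction is OR_AB / (OR_A × OR_B). A value below 1 says that the pair does better than the product of the single-agent ORs. It does not say that the pair prevents COVID-19. A pair no better than placebo has an interaction below 1 if one agent alone is harmful and the other cancels that harm. Two effective agents that act independently have an interaction of exactly 1.

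If a data monitoring committee (DMC) follows the platform text, half the arms of the final design have no numerical futility or harm boundary, and the only probability reported for them can be misread as efficacy.

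The interaction term is also written in the singular. A 2-by-2-by-2 design has three two-way terms and one three-way term. The plan does not say whether synergy for Arm 8 means the three-way term alone or all four together.

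**Working it through.** **Inputs from the plan.** OR 0.7; control rates 5%, 10%, 15% (11.2.1); equal allocation (11.3); thresholds 95% and 99% (11.5). Phase sizes from Section 3, part D, and the ceiling in 11.2.1: 10,000 / 4 = 2,500 per arm in the 4-arm phase; (30,000 − 5,000 − 10,000) / 8 = 1,875 per arm in the 8-arm phase.

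**Assumptions.** A flat prior (the plan centres the prior on 1 and leaves its spread to the SAP), a normal approximation on the log-odds scale, and a four-cell contrast for a two-agent interaction. The ORs in scenarios A to C are illustrative, except that 0.7 is the plan's own effect size.

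**1. The plan's own figure.** Control 5%, OR 0.7: treated rate 3.55%. At 2,500 per arm, SE of ln OR = √[1/(2500×0.05×0.95) + 1/(2500×0.0355×0.9645)] = 0.142. Φ(0.357/0.142 − 1.645) = 80.8%; the two-proportion formula gives 81.2%. The stated chance above 80% reproduces at 2,500 per arm (at 2,000 it is 73%). The plan gives no such figure for the combination rule.

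**2. Formula.** SE of ln(interaction) = √Σ 1/[n p(1−p)] over the four cells. P(declare synergy) = Φ(−ln(interaction)/SE − z), with z = 1.645 (95%) or 2.326 (99%).

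**3. Scenario A: combination no better than placebo.** Drug A OR 1.3, vaccine OR 1.0, combination OR 1.0. Interaction = 1/1.3 = 0.77, ln = −0.262. At 5% control and 2,500 per arm, SE = 0.179, so Φ(1.468 − 1.645) = 43%.

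| Synergy declared | 5% control | 10% | 15% |
|---|---|---|---|
| SE, 2,500 per arm | 0.179 | 0.130 | 0.110 |
| 2,500, 95% threshold | 43% | 64% | 77% |
| 2,500, 99% threshold | 20% | 38% | 53% |
| 1,875, 95% threshold | 35% | 54% | 66% |
| 1,875, 99% threshold | 15% | 28% | 40% |

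The 11.4.2 rule, applied to the same combination, would be met in about 5%.

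**4. Scenario B: two independent agents at OR 0.7.** Combination OR = 0.7 × 0.7 = 0.49, interaction 1. Synergy is declared in Φ(−1.645) = 5%. For the combination against placebo at 5% control and 2,500 per arm, SE = 0.157 and ln 0.49 = −0.713, so 11.4.2 is met in Φ(0.713/0.157 − 1.645) = 99.8%, and more often at 10% and 15%. At 1,875 per arm and 5% control it is about 99%.

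**5. Scenario C: harmful independent pair.** OR 1.25 each, combination OR 1.25 × 1.25 = 1.56, interaction 1. The interaction rule cannot flag this, and it calls the pair synergistic in about 5%. The table's P(OR≥0.9) line, applied to the combination, would be met in 99.2% to 100% of trials over 1,875–2,500 per arm and 5–15% control.

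**The case against.** A reader might infer that combination arms are judged by the interaction alone, have no efficacy criterion at all, and would be endorsed on a finding of synergy. The documents do not support that. Section 11.4.2 covers arms with more than one agent and compares each with placebo; on that rule the OR 0.49 pair is found, not missed. The opening of 11.5 refers to any active arm. The interaction criterion serves to declare synergy, and the plan nowhere says that an arm is continued or endorsed on it. A pair that acts independently should fail a synergy test about 95% of the time.

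Scenario A also leaves out the other triggers. In simulation at 2,500 per arm, among trials declaring synergy, Drug A alone also met P(OR≥0.9) above 95% in 99.4% at 5% control and in over 99.9% at 10% and 15%. Synergy without that flag is then 43% × 0.6%, about 0.3% of trials at 5% control. Synergy together with the combination meeting 11.4.2 occurred in only 2% to 4%. The OR of 1.3 is assumed, and a sceptical prior centred on 1 would lower the synergy rates.

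Section 8.9 lets the DMC stop any arm for safety, and 11.4 defers detail to a fuller SAP, which is not in these documents.

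All of this stands against the stronger reading. It does not remove the conflict. Section 11.4.2 supplies superiority only. The platform text is the more specific passage and confines the thresholds to agents given alone. The safety stop in 8.9 has no numerical threshold.

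**Conclusion.** Wrong as written, as a conflict between decision rules. Section 11.4.2 and the opening of 11.5 imply that each combination arm is judged against placebo; the platform text of 11.5 names a different quantity for those arms. On the platform text, 1 of 4 and later 4 of 8 arms lack a numerical futility or harm trigger.

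The size depends on the scenario. A combination with OR 1.0 is called synergistic in 43% to 77% of trials at 2,500 per arm and 95%, and in 15% to 40% at 1,875 per arm and the 99% interim threshold. These rates rest on assumed ORs, a flat prior and reading the printed 0.95% as 95%. That an interaction does not measure benefit against placebo needs none of those assumptions. The documents do not show that ineffective combinations would be declared effective. They leave open which rule governs, and this should be settled before the factorial phase opens.

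**What to change.** In Section 11.5:

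- State that the trigger table (benefit, futility, harm) applies to each combination arm's OR against concurrent placebo, as 11.4.2 implies, and amend the platform sentence that confines the thresholds to agents given alone.
- Keep the interaction as a separate question. Always report it beside the combination's OR against placebo, so that synergy is not read as efficacy.
- Name the interaction contrast used for Arm 8: the three-way term alone, or the three two-way terms and the three-way term together.
- Confirm that the printed 0.95% means 95%.

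The cost is wording in the protocol and SAP; the same model supplies every quantity. The downside is a few more comparisons to report and fewer unqualified claims of synergy.
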